1. SUMMARY

A registry to audit the current range of applications, technical success rate, safety profile, complication rate and efficacy of cryoablation procedures being performed in children in the United Kingdom.

2. BACKGROUND

Cryoablation involves image-guided insertion of single-use specialised needles or probes through the skin into a soft tissue or bone lesion. The base unit is connected to the probe(s) and generates cyclical freezing and thawing of the tissues at the probe tip(s) via exchange of highly pressurised gases through the probe lumen(s). Extreme freezing and thawing of the lesion causes permanent tissue destruction through both mechanical disruption of tissue membranes and one or more secondary immune responses.

Cryoablation is one of several minimally invasive ablative techniques used to reduce the size of or to eradicate soft tissue and bone lesions. Ablative techniques are now an accepted standard of care for many benign and malignant lesions in adult practice. Cryoablation is widely used in the management of renal cell carcinoma, as recognised by NICE, with long-term outcomes matching surgical resection [1].

The advantages of cryoablation over surgery, particularly in a paediatric population, are:

- Minimally invasive approach, therefore suitable for day case procedures and almost scarless
- Significantly faster recovery times compared to complex surgical debulking
- Minimal complication rates compared to surgery (less risk to nerves, blood vessels and critical solid organ)
- Affords excellent pain relief (has an independent role in chronic pain management)

To date the use of cryoablation in children remains novel and under reported [2,3].

The purpose of this registry is to audit the current range of applications, technical success rate, safety profile, complication rate and efficacy of cryoablation procedures in children. This registry will, as a minimum, clarify current practice and outcomes within individual centres, allowing teams to audit and benchmark their own procedures and aims to align practice amongst individual hospitals. A registry will provide a body of evidence to establish parameters for best practice and may highlight conditions that respond better or worse than others to this novel therapy. The audit may lead to a clinical trial for the treatment of one or more specific conditions but in the interim aims to provide evidence for the efficacy and safety of the procedure and protect against indiscriminate use of this treatment modality in children in the future.

References:

1. www.nice.org.uk/guidance/IPG402

3. AIM(S) OF STUDY

Principle aim: Establish feasibility and safety of cryoablation in children

Secondary aims: Assess response to treatment (as measured by change in lesion size and/or change in symptomatology) post treatment

4. OBJECTIVES

1. To identify all cryoablation procedures in children in our institution.
2. Invite other centres offering cryoablation in children to participate by submitting data via the online registry
3. To collect data via an online registry
4. To analyse the data to establish the safety and efficacy of this procedure in children and to identify trends in outcomes for different conditions treated
5. To establish guidelines for best practice regarding cryoablation treatment in children

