5. STUDY DESIGN

This is a prospective multi-centre, open, non-controlled repeat treatment registry and data collection in collaboration with other individual hospitals. The registry is based

with Great Ormond Street Hospital NHS Foundation Trust; other centres in the UK and Europe will be invited to participate. All such centres will be subject to their institution's audit and ethics processes

The registry will consist of a robust, multi-centre data collection system to support and establish the treatment pathway, safety parameters and outcomes of paediatric cryoablation. The registry aims to collect standardised data from all centres performing cryoablation in children to allow robust audit of this procedure and its outcomes. Multiple data sets will be collected and entered into an anonymised web-based host. The registry is designed with the patient at the centre of the data collection. Anonymised data will be analysed collectively but will ultimately be owned and retained by individual Trusts.

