9. STUDY OUTCOMES

9a. Primary Outcome

Occurrence and severity of complications arising from cryoablation treatment

9b. Secondary Outcome(s)

1. Occurrence and causes of procedural/technical failure of the procedure

2. Where relevant, change in maximal diameter of lesion following treatment, as measured on ultrasound or MRI, comparing pre-treatment diameter to diameter at 2 years.
3. Where relevant, change in symptomatology post treatment, as assessed by quality of life questionnaires and visual analog scales.
4. Where relevant, change in function post treatment, as assessed by clinical review and physiotherapy assessment.

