10. STUDY PROCEDURES

10a. Recruitment of participants

Data from all cryoablation procedures performed in our institution will be entered into the registry. Data from procedures at other UK institutions may also be submitted.

10b. Randomisation

This is a non-randomised study.

10c. Study procedure

Data will be entered into an online-based registry designed for this study. The registry is designed and managed by Obsidian Health Ltd and funded by Biocompatibles UK Ltd.

The following dataset is an indication of the data items that will be collected within the registry. The registry is not limited to these items and the items and data format can be changed before or during the registry.

Schema

- Patient
- Patient has Diagnosis
- Patient has one or more Treatments
- Patient has one or more Follow-ups
- Patient has one or more Complications
- Patient has one or more Post-ops

Data items

Data item	Data type
-----------	-----------

Patient

Patient identifier	Local pseudonym
Date of Birth (0 - 18)	Month and year only
Gender	List
Weight (Kg)	Float

ASA score (anaesthetic risk) 1 - 4	Integer
---------------------------------------	---------

Diagnosis

Diagnosis	List
Comorbidities	List
Biopsy proven?	Y/N
Snomed code	List
Lesion anatomical site: limb, thorax, head and neck, abdomen, pelvis (need more detail here)	List
Lesion tissue involvement: Fat/bone/muscle/other	List
Pre-operative information	
Length of symptoms already	Months
Imaging (MRI, US, other)	List
Symptoms	List
Other treatments tried	List
Treatment	
Treatment date	Date
Pre-op	List
Size of lesion	Float [possibly 3 floats]
Symptoms	List
No of probes	Integer
Freeze time*	Float
Thaw time*	Float
Cryoablation system probe type(s)	List [may need updating as new systems come onto market]
No. of freeze/thaw cycles	Radio
Thaw type [active or passive]	Radio
% power during freeze cycle	
*freeze and thaw time for each cycle	

Technical success	Binary
If technical success no - reason	List +/- text
Length of inpatient stay	
Any medical support required (list, such as iv analgesia)	
Immediate complications	Multi-list
Follow-up at 3 mths, 6 mths, 1 year, 2 years	
Follow-up date	Date
Imaging	List
Size of lesion	Float
Symptoms	List
Complications at follow up	
Complication	Multi-list
Onset	
Duration of problem	
Any treatment given	
Resolved?	

10e. Patient safety

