13. OUTCOMES AND SIGNIFICANCE

The results of this study will be shared with other participating centres and selected anonymised data will be made available to Boston Scientific Corporation, as owner of its subsidiary Biocompatibles UK Ltd, who fund the study. The data will be used to establish best practice. Adverse outcomes will be investigated and used to modify the technique for future procedures. The study aims to highlight any conditions that respond significantly well or not to this procedure and will promote any such findings to ensure children are offered the best treatment available.

The co-investigators plan to present the outcomes at the annual scientific meeting of the Society for Pediatric Interventional Radiology and other relevant scientific forums and publish the outcomes in relevant scientific journal(s).

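### Objective 4 promises to establish efficacy, but an uncontrolled before-after registry can only describe change after treatment

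*Protocol*

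**What the plan says.** Protocol Section 4, objective 4: "To analyse the data to establish the safety and efficacy of this procedure in children". The same item adds that trends in outcome will be sought across the conditions treated. Objective 5 follows: "To establish guidelines for best practice regarding cryoablation treatment in children".

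Section 5 gives the design: "This is a prospective multi-centre, open, non-controlled repeat treatment registry and data collection". Section 10b adds: "This is a non-randomised study".

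Section 9b lists the response outcomes. Lesion size is assessed by "comparing pre-treatment diameter to diameter at 2 years". Symptoms are assessed as "change in symptomatology post treatment, as assessed by quality of life questionnaires and visual analog scales". Function is likewise a change after treatment, judged by clinical review and physiotherapy. Complications are the primary outcome, and technical failure is the first secondary outcome.

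Section 3 words the aims more modestly. Feasibility and safety are to be established, but response to treatment is only to be assessed. Section 2 says a clinical trial may follow. Section 13 says "The data will be used to establish best practice", and that the study will identify conditions that respond particularly well or poorly and publicise those findings.

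**The concern.** To establish efficacy is to claim that the treatment caused the improvement. That needs some account of what would have happened without it. Here the only contrast available is the same child earlier and later.

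The harm would come at the reporting stage. A condition that tends to shrink or settle untreated would look like a good responder to cryoablation, and one that tends to progress would look like a poor one. Section 13 plans to publicise exactly this kind of difference. Section 2 wants the registry to guard against indiscriminate use of the technique in children, and reading uncontrolled change as proven efficacy would work against that purpose.

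**Working it through.** The protocol states no sample size, effect size, standard deviation or correlation for any response outcome, so there is no figure to reproduce. The check sets the objective beside what the design can supply.

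1. **Is there a control group?** No. Section 5 says non-controlled and Section 10b says non-randomised. No historical or natural-history comparator is named either.

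2. **Could a comparison come from within the registry?** The second exclusion criterion in Section 8b removes children who are offered another modality instead. Section 8a keeps children in whom cryoablation proved impossible, but they are selected by that very fact and the protocol does not put them forward as a comparator.

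3. **Could each child's own earlier course serve?** The dataset in Section 10c lists lesion size at treatment and then at 3 months, 6 months, 1 year and 2 years. Symptoms appear in the pre-operative and treatment blocks as list items, and symptom duration is a single number of months. None of this is a run of dated pre-treatment measurements that would show the untreated trend. Where a child has repeat treatments, sizes recorded before later sessions already follow an earlier one.

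4. **Could the analysis repair it?** Section 11 plans univariate and multivariate analysis. Adjustment among treated children can compare conditions or techniques with one another. It cannot yield a treated-versus-untreated contrast when nobody untreated is observed. Comparing conditions also mixes any difference in treatment effect with differences in natural history.

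5. **Which explanations stay open, and for which outcome?**
   - Lesion diameter, compared at baseline and 2 years: chiefly natural course.
   - Quality-of-life questionnaires and visual analogue scales: regression to the mean, if baseline scores are taken when a child is worse than average, and reporting by people who know that treatment was given.
   - Complications and technical failure: neither problem arises. These are rates among treated or attempted procedures and can be estimated without a control.

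6. **Is the objective consistent with the aims?** No. Section 3 reserves the stronger verb for feasibility and safety and uses the weaker one for response. Objective 4 applies the stronger verb to efficacy too.

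**The case against.** The strongest reply is that the protocol, read as a whole, makes no claim to a controlled treatment effect. It calls itself an audit, discloses the uncontrolled design, makes complications the primary outcome, words the response outcomes as change, and says a trial may follow. On that reading the problem is one verb. Most of this is correct: the design is legitimate for a registry and is not criticised here. What does not fall away is that objective 4 states what the analysis is for, and Section 13 turns it into findings to be published and promoted. Nor can the matter be left to an analysis plan, which cannot supply a comparator that was not collected. Section 10c does allow data items to change, but it names no such addition.

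Several stronger readings are tempting and are not supported:

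- **That objective 5 is wrong in itself.** Guidance can rest on technique, complications and technical failure, none of which needs a comparator. Section 13 speaks of adverse outcomes being used to modify technique. Only guidance resting on efficacy is affected.
- **That children are treated when symptoms are at their worst, or receive other treatments alongside.** Sections 7 and 12 speak only of a clinical decision and clinical need. Section 10c records other treatments tried, as pre-operative information. Regression to the mean is therefore something the design cannot rule out, not something the documents show.
- **That the bias can be sized.** Any figure would need an assumed correlation between repeated scores and an assumed selection of children at baseline. The protocol gives neither.
- **That a controlled trial is planned.** Section 2 says only that a clinical trial may follow.

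**Conclusion.** The point holds for the efficacy part of objective 4. With no comparator and no pre-treatment series, the registry can describe change in lesion size, symptoms and function, but it cannot attribute that change to cryoablation. The objective therefore exceeds both the design and the study's own secondary aim.

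Its reach is limited. The primary outcome and the technical-failure outcome stand as they are, and objective 5 is affected only in part. The conclusion rests on the stated design, outcomes and listed dataset, and on no numerical assumption. The size of any bias is unknown. The fault lies in the inference claimed, not in running an uncontrolled registry. It is worth correcting because it changes what may be concluded and promoted about particular conditions.

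**What to change.** - **Section 4, objective 4.** Reword to: *estimate complication and technical-failure rates and describe change in lesion size, symptoms and function after treatment*. The search for trends across conditions can stay, as description.
- **Section 13.** State that differences in response between conditions are uncontrolled before-after changes. They will be reported as descriptive and as hypotheses for the clinical trial that Section 2 says may follow, not as established efficacy. The sentence on best practice should be read under the same limit wherever it rests on efficacy.
- **Sections 1 and 2.** Align the mentions of efficacy in the same way, so that rewording objective 4 does not create a new inconsistency.

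Objective 5 needs no change beyond that limit. No outcome, data item or analysis has to be altered. The cost is an edit to the text and a less favourable stated conclusion.

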5. STUDY DESIGN

This is a prospective multi-centre, open, non-controlled repeat treatment registry and data collection in collaboration with other individual hospitals. The registry is based

with Great Ormond Street Hospital NHS Foundation Trust; other centres in the UK and Europe will be invited to participate. All such centres will be subject to their institution's audit and ethics processes

The registry will consist of a robust, multi-centre data collection system to support and establish the treatment pathway, safety parameters and outcomes of paediatric cryoablation. The registry aims to collect standardised data from all centres performing cryoablation in children to allow robust audit of this procedure and its outcomes. Multiple data sets will be collected and entered into an anonymised web-based host. The registry is designed with the patient at the centre of the data collection. Anonymised data will be analysed collectively but will ultimately be owned and retained by individual Trusts.

6. STUDY SETTING/LOCATION

The registry is based at Great Ormond Street Hospital for Children NHS Foundation Trust. Data from all cryoablation procedures will be entered in this registry. Other Trusts will be encouraged to submit data to the same registry.

7. STUDY POPULATION

All children in whom a clinical decision is made to treat with percutaneous cryoablation

8. ELIGIBILITY CRITERIA

8a. Inclusion criteria

All children in whom a clinical decision is made to treat with percutaneous cryoablation, to include those in whom cryoablation was not technically or clinically possible at any stage.

8b. Exclusion criteria

1. Subjects over the age of 18 years.
2. Any subject whose clinical management evolves so that treatment modalities other than cryoablation are offered instead.

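### Inclusion criterion 8a and exclusion criterion 8b(2) contradict each other for children in whom cryoablation proves impossible and who are then offered another treatment; applying 8b(2) overstates feasibility and can understate technical failure

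*Protocol*

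**What the plan says.** Section 7 defines the population by intention: "All children in whom a clinical decision is made to treat with percutaneous cryoablation". Section 8a repeats this and extends it explicitly, "to include those in whom cryoablation was not technically or clinically possible at any stage". Section 8b(2) then excludes "Any subject whose clinical management evolves so that treatment modalities other than cryoablation are offered instead".

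Other sections bear on the same children:

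- Section 6: "Data from all cryoablation procedures will be entered in this registry". Section 10a says the same of the lead institution: "Data from all cryoablation procedures performed in our institution will be entered into the registry".
- Section 10c lists a binary item for technical success, followed by "If technical success no - reason".
- Section 9b makes this the first secondary outcome: "Occurrence and causes of procedural/technical failure of the procedure".
- Section 3 gives the principal aim: "Establish feasibility and safety of cryoablation in children".

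**The concern.** A child for whom cryoablation was planned, found impossible and replaced by another treatment is included by 8a and excluded by 8b(2). The protocol has no rule of precedence. 8b(2) is not tied to a time point (before or after an attempt) or to a reason (impossibility, preference, new findings).

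The overlap falls on the children who carry the information about feasibility and technical failure. Whether they are counted would depend on what happened after the decision to treat, so the exclusion selects on the outcome. Centres that read the two criteria differently would also enter different children, which works against the benchmarking purpose set out in section 2. Because this is an entry rule in a prospective registry, a child who is left out cannot be recovered at the analysis stage.

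**Working it through.** **Does any reading remove the conflict?**

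| Reading of 8b(2) | Children removed | Conflict with the rest of the protocol |
|---|---|---|
| Broad: any switch, including after an attempt | Children never attempted and switched; failed attempts that are switched | 8a; section 7; the all-procedures statements in sections 6 and 10a; the failure-reason item in 10c |
| Narrow: plan changed before any attempt | Children found unsuitable beforehand and switched | 8a, whose extension covers clinical impossibility at every stage; section 7, which makes no exception |

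The conflict remains on both. On neither reading does 8b(2) reach failures that are treated again with cryoablation or are not switched.

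**Direction of the bias.** The protocol states no failure, switch or complication rate, so there is no figure to reproduce. Take N children with a decision to treat, of whom F fail and x are failed, switched and excluded. The failure rate moves from F/N to (F − x)/(N − x), which is lower whenever x > 0 and F < N. The success rate moves from (N − F)/N to (N − F)/(N − x), which is higher.

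**Size, for illustration. All inputs below are assumed.**

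*Technical failure per attempt (broad reading).* Let f be the true failure share and s the share of failures switched and excluded. Observed failure = f(1 − s)/(1 − fs).

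| True f | s = 50% | s = 80% | s = 100% |
|---|---|---|---|
| 5% | 0.025/0.975 = 2.6% | 0.010/0.960 = 1.0% | 0% |
| 10% | 0.050/0.950 = 5.3% | 0.020/0.920 = 2.2% | 0% |
| 20% | 0.100/0.900 = 11.1% | 0.040/0.840 = 4.8% | 0% |

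*Feasibility per 100 decisions to treat.* Suppose 10 children are never attempted and 90 are attempted, of whom 9 fail and 81 are completed. True feasibility is 81/100 = 81%. Here s is the share switched and excluded within each group that the reading reaches.

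| Reading | Formula | s = 50% | s = 80% | s = 100% |
|---|---|---|---|---|
| Narrow | 81/(100 − 10s) | 81/95 = 85.3% | 81/92 = 88.0% | 81/90 = 90.0% |
| Broad | 81/(100 − 19s) | 81/90.5 = 89.5% | 81/84.8 = 95.5% | 81/81 = 100% |

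*Complications per 100 attempts (broad reading).* Suppose 10 failures have complication risk r, 90 other attempts have risk 10%, and 8 of the 10 failures are excluded. True rate = (10r + 9)/100; observed rate = (2r + 9)/92.

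| r | True | Observed |
|---|---|---|
| 0% | 9.0% | 9/92 = 9.8% |
| 10% | 10.0% | 9.2/92 = 10.0% |
| 30% | 12.0% | 9.6/92 = 10.4% |

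The error changes sign with r, so its direction for the primary outcome is not determined.

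**The case against.** The strongest reply is that the two rules can be separated by reason: 8a covers impossibility, while 8b(2) covers a decision that was replaced for some other cause. It can be added that after a failed attempt cryoablation was in fact offered and performed, so a later treatment follows it and does not stand in its place. Sections 6 and 10a already require all procedures to be entered. On that view attempted failures stay in, technical failure and complications are untouched, and only feasibility is affected, for which section 9 defines no rate. The illustrative figures rest wholly on assumed inputs, and the columns with every failure switched give 0% by construction. The denominators could be left to an analysis plan. Finally, this is an uncontrolled audit registry with no hypothesis test.

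Part of this stands. The technical-failure and complication figures apply only if 8b(2) is read broadly; the feasibility percentage is a natural summary of the principal aim, not a statistic the protocol names; and the magnitudes are not estimates. Choice of denominator is secondary to the point.

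The rest does not remove the contradiction. The separation by reason is not in the text. Even if it were adopted, children switched for other reasons would still belong to the decision-to-treat population of sections 7 and 8a. The statements in sections 6 and 10a argue for keeping attempted failures, but they do not say that they override an exclusion criterion. An analysis plan cannot restore children who were never entered.

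**Conclusion.** The concern holds, and the criteria must be corrected. Two stated rules in the same section assign the same child both to the registry and out of it, and no reading found in the text reconciles them. Where 8b(2) is applied, the direction is certain: apparent feasibility rises on either reading, and the technical failure rate falls if switched failed attempts are dropped. The size depends on how often impossible cases are switched, which the protocol does not state. On the assumed inputs, true feasibility of 81% would appear as 85.3% to 90.0% on the narrow reading and as 89.5% to 100% on the broad one. No direction can be claimed for the primary outcome.

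**What to change.** Delete 8b(2), or reword it so that it removes no child who meets 8a. Keep every child with a decision to treat in the registry, with a disposition (not attempted; attempted and not completed; completed) and a reason. The schema in 10c expects at least one treatment per patient, so it should allow a record without one for children never attempted; 10c already permits changes to the data items.

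It would help to state the denominators at the same time: all decision-to-treat children for feasibility, and all attempted cases, whatever treatment follows, for technical failure and complications.

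The cost is one sentence in 8b and one status field. Centres would have to log children in whom cryoablation was never attempted, and the reported feasibility and technical success rates may look slightly less favourable. The change concerns who is counted and alters no child's care.
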